12.6 Translational Studies

We plan to correlate the tumor markers (MSI, tissue PDL1 expression, mutational load, genomic mutation analysis, BIM/PD-1 expression in tumor infiltrating T cells, and other immune markers, and tumor tissue of origin testing) and plasma-based markers (soluble PD-L1 and T cell subpopulations) with clinical endpoints like confirmed response, best responding abscopal lesion, time-to-event outcomes, and adverse events. Statistical and graphical techniques will be used to evaluate the relationships between tumor markers and clinical data. For time-to-event endpoints, we will use Cox proportional hazards models, and for confirmed response we will use Logistic regression models. In addition, we will use the Chi-square or Fisher's exact tests to test the association between categorical marker data and confirmed response/adverse events. Continuous marker data will be assessed using 2-sample t-tests (or the nonparametric equivalent for non-normal data). Descriptive statistics and graphical techniques will be used to summarize this data. Given the small sample size, all these analyses will be considered hypothesis generating and exploratory.

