2.1.3 Correlative/Exploratory Objectives

- Evaluate the association of MSI status and mutation load with clinical efficacy
- Evaluate the association of tissue PDL1 expression with clinical efficacy
- Evaluate the association of soluble PD-L1 with clinical efficacy
- Evaluate changes in the CD11a^{high} PD-1^{high} CD8+ T effector population in association with pembrolizumab-based therapy
- Evaluate changes and predictive value of BIM expression in T cells in circulation and the predictive value of BIM/PD-1 expression in tumor infiltrating lymphocytes
- Evaluate the prognostic and predictive value of tumor tissue of origin testing

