9.4 Measurement of Effect per RECIST 1.1

9.4.1 Target Lesions & Target Lymph Nodes

Measurable lesions up to a maximum of 5 lesions, representative of all involved organs, should be identified as “Target Lesions” and recorded and measured at baseline. Lesions to be monitored for assessment of response must lie outside the RT field. These lesions can be non-nodal or nodal, where no more than 2 lesions are from the same organ and no more than 2 malignant nodal lesions are selected. **NOTE:** If fewer than 5 target lesions and target lymph nodes are identified (as there often will be), there is no reason to perform additional studies beyond those specified in the protocol to discover new lesions.

Target lesions and target lymph nodes should be selected on the basis of their size, be representative of all involved sites of disease, but in addition should be those that lend themselves to reproducible repeated measurements. It may be the case that, on occasion, the largest lesion (or malignant lymph node) does not lend itself to reproducible measurements in which circumstance the next largest lesion (or malignant lymph node) which can be measured reproducibly should be selected.

Baseline Sum of Dimensions (BSD): A sum of the longest diameter for all target lesions plus the sum of the short axis of all the target lymph nodes will be calculated and reported as the baseline sum of dimensions (BSD). The BSD will be used as reference to further characterize any objective tumor response in the measurable dimension of the disease.

Post-Baseline Sum of the Dimensions (PBSD): A sum of the longest diameter for all target lesions plus the sum of the short axis of all the target lymph nodes will be calculated and reported as the post-baseline sum of dimensions (PBSD). If the radiologist is able to provide an actual measure for the target lesion (or target lymph node), that should be recorded, even if it is below 0.5 cm. If the target lesion (or target lymph node) is believed to be present and is faintly seen but too small to measure, a default value of 0.5 cm should be assigned. If it is the opinion of the radiologist that the target lesion or target lymph node has likely disappeared, the measurement should be recorded as 0 cm.

The minimum sum of the dimensions (MSD) is the minimum of the BSD and the PBSD.

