9.5 Response criteria per best abscopal response

A novel aspect of this study is the examination of best abscopal response. Response criteria per best abscopal response are identical to RECIST-defined response criteria, with the exception that tumor shrinkage by > 20% in only a single representative measurable lesion (not a sum of lesions) is sufficient to count as a best abscopal response. In addition, up to 10 measurable lesions per organ may be recorded. Best abscopal response is a binary variable: present or not present. A subject can experience a best abscopal response at the same time as CR, PR, SD, or PD as defined by irRECIST/RECIST 1.1.

See 9.2.2 for guidance on management of cases when a best abscopal response co-occurs with PD as defined by irRECIST/RECIST 1.1.

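### Every method Section 12.6 names for relating markers to tumour shrinkage uses a yes/no response; a rank analysis of measured best-lesion change would be a cheap, usually more powerful addition

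*Combined protocol and SAP*

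**What the plan says.** Section 2.1.3 sets the correlative objectives in general terms, for example "Evaluate the association of soluble PD-L1 with clinical efficacy". Section 12.6 then says markers will be correlated "with clinical endpoints like confirmed response, best responding abscopal lesion, time-to-event outcomes, and adverse events". The methods it names are:

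- Time-to-event endpoints: Cox models.
- Response: "for confirmed response we will use Logistic regression models".
- Categorical markers: "we will use the Chi-square or Fisher's exact tests to test the association between categorical marker data and confirmed response/adverse events".
- Continuous markers: a two-sample t-test or its nonparametric equivalent. The grouping variable is not stated, but such a test needs two groups.

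The best responding abscopal lesion is in the endpoint list, but no method is tied to it. Section 9.5 adds: "Best abscopal response is a binary variable: present or not present".

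The measurements behind that binary call are collected. Section 9.5 allows up to 10 measurable lesions per organ to be recorded. Section 9.4.1 requires baseline and post-baseline sums of target dimensions outside the RT field (BSD and PBSD), and says "The BSD will be used as reference to further characterize any objective tumor response in the measurable dimension of the disease". Section 12.6 closes by calling all the marker analyses exploratory.

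**The concern.** A yes/no outcome treats a patient whose best lesion shrank by 29% the same as one whose lesions all grew. For the primary endpoint the cut is needed, because the result is compared with a historical response rate. The marker analyses have no historical comparator, so nothing in the documents requires the cut there.

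With few responders, splitting at the cut discards much of the information in the diameters. At stake is how well 29 patients can generate hypotheses about who benefits. The trial's go/no-go decision is not affected.

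**Working it through.** **Inputs from the documents.** Evaluable N = 29 (12.3). Null and alternative response rates 9% and 24%, one-sided alpha 0.10, power 80%, continue at 2 or more of 14, success at 5 or more of 29 (12.2.1). PD-L1-expressing cells in 21% of CUP tumours (1.3). The documents give no power, alpha or effect size for the marker analyses.

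**The plan's own figure.** The probability of declaring success is the sum over x = 2 to 14 of P(X1 = x) × P(X2 ≥ 5 − x), with X1 ~ Bin(14, p) and X2 ~ Bin(15, p). This gives 0.0975 at p = 0.09 and 0.806 at p = 0.24. The chance of stopping early at 9% is 0.91^14 + 14 × 0.09 × 0.91^13 = 0.267 + 0.370 = 0.637. The primary design is reproduced.

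**Responders available to the marker tests.** 0.24 × 29 = 6.96, about 7, at the alternative; 0.09 × 29 = 2.6 at the null. The success threshold is 5.

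**Power comparison (simulation).** Assumptions not in the documents: marker and tumour change are bivariate normal with correlation rho; response is the top 24% of that same change; the worst 20% are tied at the worst rank to stand for patients without a post-baseline scan; two-sided 0.05. The requirement to confirm response is not modelled. Ranges cover repeated independent runs.

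| rho | t-test of marker by response | Spearman on measured change |
|---|---|---|
| 0 | about 5% | about 5% |
| 0.3 | 20–21% | 31–32% |
| 0.4 | 33–34% | 52–53% |
| 0.5 | 48–52% | 74–77% |

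**Sensitivity of the gain.**

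- *Binary marker at 21% prevalence*, response 51.4% versus 16.7% (0.21 × 0.514 + 0.79 × 0.167 = 0.24): Fisher 33%, rank-sum on measured change 49%.
- *Fewer responders (17%, close to 5/29)*: 30% versus 53% at rho 0.4, and 42% versus 74% at rho 0.5.
- *20% unscanned, counted as non-responders in the t-test but dropped from a Pearson analysis of change*: 17% versus 28% at rho 0.3, 27% versus 49% at 0.4, 41% versus 72% at 0.5.
- *Marker acts only at the response threshold* (1 SD shift in responders, none unscanned): t-test 57%, Spearman 31%. The yes/no test is better here.
- *Analysing the summed dimensions when the marker tracks only the best lesion* (rho 0.5, t-test about 50%): Spearman on the sum has 58%, 53% and 46–48% power if lesion and sum correlate at 0.8, 0.7 and 0.6 with 20% tied worst. With no ties it has 55%, 42% and 32%. If the marker acts on all lesions alike, both measures keep the gain.

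The last item decides which measure to use. The gain in the table belongs to the measure that defines response, which in this trial is the single best non-irradiated lesion (9.2.1, 9.5, 12.2.1).

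**The case against.** **The plan does not rule out a measured-change analysis.** A reader might infer that shrinkage can enter only as yes/no. The text does not go that far. Section 12.6 introduces its endpoints as examples, lists the best responding abscopal lesion separately from confirmed response, and allows unspecified statistical and graphical techniques. What stands is narrower: no named method uses the measured change, and the listed endpoint has no method, outcome scale or rule for missing scans.

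**Markers do not depend on shrinkage alone.** A reader might infer that false-negative biomarker conclusions are likely. That is not supported. Cox models on time-to-event endpoints are also planned, Section 1.1 puts second-line survival at 3 to 5 months so events should be frequent, and no alpha or negative conclusion is attached to any marker.

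**The summed dimensions might look like the natural continuous outcome.** They are a different construct. Section 9.5 counts shrinkage in one lesion and lets it coexist with stable or progressive disease, and Section 1.2.2.3 explains why mixed responses matter. This objection stands, so the sum belongs in a sensitivity analysis.

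**The effect sizes are assumed.** True. The gain should be read as a range under stated conditions, not as a fixed number of power points.

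**Conclusion.** The point holds as a cheap improvement of low severity. As written, every named marker-to-shrinkage method uses a yes/no response, with about 7 responders expected at the design alternative, while the diameters for a finer analysis are already recorded. If the marker relates monotonically to best-lesion shrinkage at a correlation of 0.3 to 0.5, a rank analysis raises power from about 20–50% to about 32–74%. This rests on an assumed correlation, a normal model and two-sided 0.05. It can shrink or reverse for a threshold-only marker or a different measure such as the sum, which is why the yes/no analyses should stay.

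A secondary reason to add it is that the yes/no cut is not consistent: Sections 9.2.1 and 12.2.1 use at least 30%, Section 9.5 uses more than 20%, and Section 9.2.1 gives no percentage for nodes. Those sections must be reconciled in any case; a percentage-change outcome does not depend on the cut.

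**What to change.** In Section 12.6:

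1. Add, for each marker, an analysis of best percentage change from baseline in the best-responding non-irradiated measurable lesion (longest diameter, or short axis for nodes). Use Spearman correlation for continuous markers and the Wilcoxon rank-sum test (Kruskal-Wallis for more than two groups) for categorical ones.
2. Rank patients with no post-baseline scan because of death or progression as worst, and state how scans missing for other reasons are handled.
3. Report percentage change in the summed target dimensions (BSD to PBSD) as a sensitivity analysis, because best-lesion change depends on how many lesions are measured.
4. Keep the logistic, Chi-square/Fisher and t-test analyses of confirmed response alongside.

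Leave the primary endpoint and the 2/14 and 5/29 rules unchanged. The cost is a few lines of text and a little programming, with no new data, visits or patients. The downside is one more exploratory outcome per marker.

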12.7 Interim Analysis/Criteria for Stopping Study

Interim Analysis (based on primary endpoint): Enroll 14 eligible patients. If at least 2 confirmed responses are observed in the first 14 eligible patients, we will continue the trial to the second stage and continue the study to a full accrual of 29 eligible patients. Otherwise, the study will be permanently closed due to lack of efficacy. Accrual will continue during the interim analysis phase unless we observe a much higher than expected accrual rate or toxicity rate.

Final Analysis (based on primary endpoint): If the trial is a success during the interim analysis, we will enroll another 15 eligible patients to the second and final stage (29 eligible total). If at least 5 confirmed responses are observed in the first 29 eligible patients (17%), the treatment will be considered worthy of further investigation. Otherwise, the study will be permanently closed due to lack of efficacy.

Adverse Event Stopping Rule: The stopping rule specified below is based on the knowledge available at study development. We note that the Adverse Event Stopping Rule may be adjusted in the event of either (1) the study re-opening to accrual after any temporary suspension or (2) at any time during the conduct of the trial and in consideration of newly acquired information regarding the adverse event profile of the treatment(s) under investigation. The study team may also choose to suspend accrual because of unexpected adverse event profiles that have not crossed the specified rule below.

Accrual will be temporarily suspended to this study if at any time we observe events considered at least possibly related to study treatment (i.e., an adverse event with attribute specified as "possible", "probable", or "definite") that satisfy any of the following criteria:

- If at any time, 4 of the initial 10 treated patients or 40% or more of all patients (i.e. when accrual is greater than 10 patients) have experienced a Grade 4 non-hematologic adverse event.
- If at any time, 2 of the initial 10 treated patients or 20% or more of all patients (i.e., when accrual is greater than 10 patients) have experienced a Grade 5 adverse event (non -progressive disease).

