12.2.2 Definition and Analysis of Secondary Endpoints

- Response rate (RR) by RECIST 1.1.
- Adverse events: The maximum grade for each type of adverse event will be summarized using CTCAE version 4.0. The frequency and percentage of grade 2+ adverse events will be assessed. We will also explore the treatment related adverse events as well (toxicities).
- Progression-free survival (PFS) is defined as the time from registration to the first of either disease progression or death from any cause, where disease progression will be determined based on RECIST 1.1 criteria. PFS will be estimated using the Kaplan-Meier method, where patients that are alive and progression-free will be censored on their last tumor evaluation date.
- Overall Survival (OS) is defined as the time from registration to death from any cause. OS will be estimated using the Kaplan-Meier method.
- Time-to-Progression (TTP) is defined as the time from registration to disease progression, where patients that are progression-free will be censored on their last tumor evaluation date. TTP will be estimated using the cumulative incidence method, where deaths will be treated as competing risks.
- Disease Control Rate (DCR) is defined as the frequency (%) of patients who have a best response of PR, CR, or Stable disease.
- The association between RR (using RECIST 1.1 (informed by irRECIST)) with other clinical endpoints (e.g., OS, PFS, etc.) will be performed. For time-to-event endpoints, we will use Cox proportional hazards models and Kaplan-Meier methodology. This analysis of RR as a predictor of OS, PFS, etc. will be based on a landmark analysis at various time points of interest post-baseline that correspond to expected tumor assessment time points. This will eliminate the possible response bias of patients living longer or doing better because they lived long enough to respond to treatment. For any associations of RR with categorical data, we will use Chi-square or Fisher's exact tests along with logistic regression models. Descriptive statistics and graphical techniques will be used to summarize this data. Given the small sample size, all these analyses will be considered hypothesis generating and exploratory.

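### The Grade 4 stopping criterion leaves out Grade 5 events, so turning one of four Grade 4 events into a death removes the automatic suspension

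*Combined protocol and SAP*

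**What the plan says.** The Adverse Event Stopping Rule in Section 12.7 of the combined protocol and SAP suspends accrual temporarily when "events considered at least possibly related to study treatment" occur "that satisfy any of the following criteria". There are two criteria:

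- First: "4 of the initial 10 treated patients or 40% or more of all patients" "have experienced a Grade 4 non-hematologic adverse event".
- Second: "2 of the initial 10 treated patients or 20% or more of all patients" "have experienced a Grade 5 adverse event", where deaths from progressive disease are not counted.

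The percentage form applies once accrual exceeds 10. The first criterion names Grade 4 with nothing such as *or higher* after it, and neither criterion combines the grades. Where the plan means a grade and everything above it, it can say so: for the secondary safety summary, Section 12.2.2 states "The frequency and percentage of grade 2+ adverse events will be assessed".

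Section 12.7 also gives some discretion: "The study team may also choose to suspend accrual because of unexpected adverse event profiles that have not crossed the specified rule below". It allows the rule itself to be adjusted during the trial in the light of new adverse event information. It gives no operating characteristics for the safety rule.

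**The concern.** A mandatory safety boundary should never become harder to cross because an outcome was worse. This one does. Take four patients with qualifying Grade 4 events and let one of those events be fatal instead. The Grade 4 count falls below its threshold, and a single death does not reach the Grade 5 threshold. Having a separate Grade 5 criterion does not help, because one death among the first 10 is exactly the case it leaves uncovered.

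This matters more than usual here. Section 1.4.2 says that lung or liver RT combined with pembrolizumab has had little safety study and makes it a focus of the trial. The same section reports Grade 3, Grade 4 and fatal lung events with pembrolizumab alone. A mixture of Grade 4 and Grade 5 events is a natural form for excess toxicity to take, and it is the form that the rule handles worst.

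**Working it through.** **Inputs from Section 12.7.** First criterion: 4/10 = 40%. Second criterion: 2/10 = 20%. The counts and percentages agree. Let *a* be the number of patients whose worst qualifying event is Grade 4 and *b* the number with a qualifying Grade 5 event.

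**First 10 patients.**

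- As written: suspend if *a* ≥ 4 or *b* ≥ 2.
- With Grade 5 counted in the first criterion: suspend if *a* + *b* ≥ 4 or *b* ≥ 2.

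| Grade 4 (*a*) | Grade 5 (*b*) | As written | Grade 4 or higher |
|---|---|---|---|
| 4 | 0 | suspend (4 ≥ 4) | suspend |
| 3 | 1 | no suspension (3 < 4, 1 < 2) | suspend (3 + 1 = 4) |

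Enumerating every pair (*a*, *b*) with *a* + *b* ≤ 10 shows that (3, 1) is the only one whose outcome differs between the two rules.

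**After 10 patients.** The thresholds are 40% and 20% of *n*, rounded up. The third column gives the largest counts that meet neither criterion at that *n*, provided that none was met earlier.

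| *n* | Thresholds (Grade 4, Grade 5) | Largest counts with no suspension | Share with Grade 4 or 5 |
|---|---|---|---|
| 20 | 8, 4 | 7 + 3 | 10/20 = 50% |
| 29 | 12, 6 | 11 + 5 | 16/29 = 55% |

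At *n* = 29, 12 Grade 4 patients and no deaths (41%) suspend accrual, while 11 Grade 4 patients and 5 deaths (55%) do not.

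**Probability of suspension by patient 29.** The documents give no expected Grade 4 or Grade 5 rates for the combination, so the rates below are assumptions. Each patient independently has a worst grade of 4, a worst grade of 5, or neither; all qualifying events are taken as non-hematologic. The rule is applied after every patient, with the fixed counts up to 10 and the percentages from 11 to 29. The probabilities come from an exact recursion over (*a*, *b*).

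| Assumed Grade 4 / Grade 5 rate | As written | Grade 4 or higher | Difference (points) |
|---|---|---|---|
| 5% / 2% | 0.018 | 0.020 | about 0.2 |
| 10% / 3% | 0.051 | 0.064 | 1.3 |
| 20% / 5% | 0.235 | 0.322 | about 9 |
| 25% / 5% | 0.364 | 0.480 | about 12 |
| 30% / 10% | 0.666 | 0.814 | about 15 |

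Continuing to the planned maximum of 34 patients changes little (25%/5%: 0.37 as written, 0.49 with the change).

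**The missed pattern alone.** At 25%/5%, the probability of exactly 3 Grade 4 and 1 Grade 5 in the first 10 is 10!/(3! 1! 6!) × 0.25³ × 0.05 × 0.70⁶ = 840 × 0.015625 × 0.05 × 0.117649 = 0.077.

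**Sensitivity to how deaths are recorded.** Suppose half of the patients who die also have a separate qualifying Grade 4 event and so already count toward the first criterion. The as-written probabilities then rise to 0.28 at 20%/5% and 0.42 at 25%/5%. The change still takes them to 0.32 and 0.48, so about half of the gain remains.

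**The case against.** The strongest reply is that the gap is narrow and that other oversight surrounds it.

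- **Discretion.** Section 12.7 lets the study team suspend below the rule, so the gap concerns automatic suspension only. That is correct. But the power is optional and is worded for unexpected profiles, while Section 10.1.7 lists pneumonitis and hepatitis as identified risks. The likeliest serious toxicities may not fit the clause.
- **Reporting and review.** Grade 4 and 5 serious events are notified within 24 hours (Section 11.2.2.1), and the sponsor-investigator gets a summary within one business day (Section 11.4). A related death would be seen quickly. Being seen does not oblige anyone to suspend. The DSMB must meet only every 6 months (Section 13.2). At 1.5 patients a month (Section 12.3), 6 × 1.5 = 9 patients could enter between meetings, and the DSMB works from these same stopping-rule data.
- **Reading of the text.** The first criterion asks whether patients have experienced a Grade 4 event, not what their worst grade was. A patient with a distinct Grade 4 event before death would count. This stands, and it shrinks the effect as shown in the working. It does not cover an event recorded only at its final grade, and Section 12.2.2 summarises each event type by maximum grade.
- **Rates.** The effect is material only when toxicity is high. The grade-specific figures in Section 1.4.2 for pembrolizumab alone are far lower, for example 0.1% for Grade 4 pneumonitis. They cover selected events and not the combination. A stopping rule exists for the case where toxicity proves higher than expected.

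**Conclusion.** The concern holds. As worded, the mandatory rule responds in the wrong direction to severity: 4 Grade 4 patients in the first 10 suspend accrual, and 3 Grade 4 patients plus 1 treatment-related death do not. The gap widens with accrual.

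The conclusion rests on two conditions: the Grade 4 events are non-hematologic and at least possibly related to treatment, and the patient who died had no separate qualifying Grade 4 event. It concerns automatic suspension, not what the team might choose to do. The probabilities depend on assumed toxicity rates and are illustrative; the ordering defect does not depend on them. If the authors always meant Grade 4 and above, the text does not say so. This should be corrected, although it affects a limited set of outcomes.

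**What to change.** In the first criterion of the Adverse Event Stopping Rule in Section 12.7, replace *a Grade 4 non-hematologic adverse event* with *a Grade 4 or higher non-hematologic adverse event*. Leave both thresholds and the separate Grade 5 criterion as they are. A death then counts toward both criteria, and 3 Grade 4 plus 1 Grade 5 gives 4/10 = 40% and suspends accrual. A fatal hematologic event would still count only under the second criterion.

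The cost is two added words and a slightly higher chance of a suspension that is in any case temporary: about 0.2 points at assumed rates of 5%/2% and 1.3 points at 10%/3%.
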